## Statistical Analysis Plan

### Primary Outcomes

All caregivers—regardless of randomized study condition—complete questionnaires on four separate occasions during this study: baseline, 3-months, 6-months, and 9-months. The four outcome measures include changes over the 9-month study period for the following scales: Zarit Burden Interview-Short Form, a questionnaire measuring caregiver burden (Zarit, Reever, & Bach-Peterson, 1980). 12 items are rated on 0-4 scale. Range: 0-48. No subscales. Higher scores represent worse outcomes; Center for Epidemiological Studies Depression Scale (CES-D), a questionnaire measuring depression (Radloff, 1977). 20 items are rated on a 0-3 scale and summed (range = 0-60). There are no subscales. Higher scores represent worse outcomes. The clinical cut-off is usually set at a score of 16; Beck Anxiety Inventory (BAI), a questionnaire measuring anxiety (Beck, Epstein, Brown, & Steer, 1988). 20 items are rated on a 0-3 scale and summed (range= 0-60). Higher scores indicate worse outcomes. There are no subscales. A score greater than 36 is considered to be clinically significant.; and Satisfaction with Life Scale, a questionnaire measuring overall life satisfaction and well-being (Diener, Emmons, Larsen, & Griffin, 1985). 5 items scored on a 1-7 scale and summed (Range = 5-35). Lower scores indicate worse outcomes. A score of 20 is considered neutral with higher scores considered increasingly more satisfied and lower scores considered increasingly more dissatisfied.

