### Statistical Methods

*Design:* Caregivers will be randomized into two groups: Experimental In-Home Technology System and Limited In-Home Technology System. Subjects will be randomized 1:1. Randomization of participants in each group will be determined by members (i.e., graduate students listed in this protocol) of the research team and staff members completing the installation will not be aware of which group the caregivers are assigned to. With a total N of 80 caregivers in two conditions and measures repeated four times, a comparison between groups using ANOVA will have .80 power to detect a medium effect size at  $p=.05$ .

*Analysis:* Descriptive statistics will be used to summarize all the clinical characteristics and demographic outcomes. These will be summarized overall, by treatment group, by assessment time, and by treatment group and time. Continuous variables will be summarized using means, standard deviations, and ranges. Categorical data will be summarized by number and percent. To evaluate the treatment effects, we will use repeated measures ANCOVAs. The respective baseline measure of each outcome variable will be included as a covariate in the appropriate analysis (e.g., baseline depression scores from the baseline measurement of the CES-D, will be used as a covariate in examining treatment effects of depression). The other predictors will be treatment group, and time (baseline, 6-months, and 9- months for caregiver outcomes). To

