evaluate treatment effects, an interaction term between treatment group and time will be included to examine treatment group-related differences controlling for baseline to later assessments for each outcome. Each significant interaction will be followed up with paired t-tests to examine treatment differences at each set of time points. Although this study involves 4 outcomes, we do not plan formal multiple comparison adjustments if the results fit a coherent pattern that is consistent with the context of similar studies. In this case, each result will reinforce the other, rather than detracting from one another, as required by formal multiple comparisons adjustments such as Bonferroni. Conversely, if only one or a very few measures reach statistical significance and their directions and/or magnitudes do not coherently fit with our prior expectations, then we will note that the result(s) with  $p < 0.05$  lack plausibility and could be due to chance, despite meeting the conventional cutoff for statistical significance.

*Missing Data:* If subjects either cannot or refuse to complete surveys we will use a sensitivity analysis approach in dealing with these missing data by performing analysis with 2 versions of scores: 1) with missing item interpolated using mean replacement by group, and 2) only using responses with 0% missing data. If the results differ for the two approaches, then we will report on the differences.

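### The SAP's only power figure (.80) is for a between-groups comparison; the group-by-time interaction that evaluates treatment has none

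*SAP*

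**What the plan says.** The Design paragraph of the SAP's Statistical Methods section holds the only power statement in either document. "With a total N of 80 caregivers in two conditions and measures repeated four times", it says, "a comparison between groups using ANOVA will have .80 power to detect a medium effect size" at the .05 level. Allocation is equal ("Subjects will be randomized 1:1").

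The Analysis paragraph of the same section describes a repeated measures ANCOVA. On the covariate: "The respective baseline measure of each outcome variable will be included as a covariate in the appropriate analysis". On the remaining terms: "The other predictors will be treatment group, and time (baseline, 6-months, and 9- months for caregiver outcomes". The treatment question is then attached to one term: to "evaluate treatment effects, an interaction term between treatment group and time will be included to examine treatment group-related differences". What follows depends on that term: "Each significant interaction will be followed up with paired t-tests to examine treatment differences at each set of time points".

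Under Primary Outcomes, caregivers "complete questionnaires on four separate occasions during this study: baseline, 3-months, 6-months, and 9-months", so the 3-month visit is collected but is not among the model's time levels.

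The SAP gives no number for a medium effect, no between-visit correlation and no expected shape of benefit over time. It does not say how the treatment-group term will be used. The protocol has no power or sample-size statement.

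**The concern.** A group main effect and a group-by-time interaction ask different questions. The first asks whether the arms differ on average over the occasions; the second asks whether the difference changes between occasions. They draw on different variance components: a higher between-visit correlation lowers the power of the first and raises that of the second. A power figure for one does not carry over to the other.

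The interaction is the term the SAP names for evaluating treatment, and it decides whether follow-up tests are run on each of the four outcomes. A reader of the results could take .80 as the chance that this test had of finding a medium benefit, and read a non-significant interaction in that light. The SAP does not support that reading.

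The interaction also cannot be powered until it is defined. Its power depends heavily on whether baseline is a time level or only the covariate, and the text makes it both.

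**Working it through.** **Inputs from the SAP:** N = 80, 1:1 (40 per arm), four measures in the power sentence, three time levels in the model (baseline, 6 and 9 months), level .05, stated power .80.

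**Assumptions, because the documents are silent:** two-sided test; medium means f = .25, that is .5 SD; equal correlation ρ between visits, .5 unless varied; no dropout unless stated. Two shapes of benefit, both .5 SD at 9 months: a step (.5 SD at every follow-up visit) and a linear build-up (.167, .333 and .5 SD at 3, 6 and 9 months). Power is from the noncentral F distribution with noncentrality λ.

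**1. The SAP's own figure.** For the group main effect over m measures, λ = f²·N·m / [1 + (m − 1)ρ], df 1 and N − 2. With m = 4: λ = .0625 × 80 × 4 / 2.5 = 8.0, power .798. At ρ = .3 it is .893 and at ρ = .7 it is .708. So .80 fits the comparison it names at ρ = .5. Here the .5 SD difference is an average over all four occasions, baseline included.

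**2. The interaction over the SAP's listed levels.** Without the covariate, λ = (N/4)·Σ(d_t − d̄)² / (1 − ρ), df 2 and 156, where d_t is the difference between arms at time t.
- Step (0, .5, .5): sum of squares .1667; λ = 20 × .1667 / .5 = 6.67; power .624.
- Build-up (0, .333, .5): sum of squares .1296; λ = 20 × .1296 / .5 = 5.19; power .511.

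With a covariate-by-time term, 20,000 simulated trials per setting give .734 and .606 (type I error .050 to .055).

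**3. If medium means f = .25 for the interaction itself, three levels.** The answer depends on the convention:
- λ = f²·N = 5.0: power .50 (.43 with four levels).
- λ = f²·(N − 2)(m − 1) = .0625 × 156 = 9.75: power .797. With four levels, .0625 × 234 = 14.6: .905.
- λ = f²·N·m / (1 − ρ) = .0625 × 80 × 3 / .5 = 30: power above .99. This implies a 9-month difference of 1.06 SD (step) or 1.20 SD (build-up).

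**4. If baseline is only the covariate (6 and 9 months remain).** For a constant benefit, Σ(d_t − d̄)² = 0, so λ = 0 and interaction power is .05 at any N or effect size. For build-up, the sum of squares is .0139, λ = 20 × .0139 / .5 = .556, df 1 and 78, power .114.

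**5. The baseline-adjusted group difference averaged over 6 and 9 months.** Variance factor V = (1 + ρ)/2 − ρ² = .75 − .25 = .50; λ = (N/4)·Δ²/V, df 1 and N − 3.
- Step, Δ = .5: λ = 20 × .25 / .50 = 10.0, power .878.
- Build-up, Δ = (.333 + .5)/2 = .417: λ = 20 × .1736 / .50 = 6.94, power .740.

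Solving for .80 power gives Δ = .449 SD with 80 caregivers, or .503 SD with 64 (80 × .8, an assumed 20% loss).

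**6. Side by side, N = 80 (step / build-up).** V is .56, .50, .36 and .26 down the rows.

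| ρ | Interaction, no covariate | Interaction, covariate-by-time | Adjusted 6/9-month average |
|---|---|---|---|
| .3 | .48 / .38 | .62 / .49 | .84 / .69 |
| .5 | .62 / .51 | .73 / .61 | .88 / .74 |
| .7 | .85 / .74 | .90 / .79 | .96 / .87 |
| .8 | .96 / .90 | .97 / .92 | .99 / .95 |

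The averaged test has more power in every row, for both shapes.

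**The case against.** The strongest reply is that no error or harm has been shown. The SAP says plainly that .80 belongs to a between-groups comparison, the arithmetic is sound for that comparison, and every interaction figure above rests on assumptions from outside the documents. Most of this stands. A reader might infer that the trial is underpowered. The documents do not support that: depending on correlation, shape and effect-size convention, interaction power can fall well below .80 or exceed .90.

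A reader might also infer from step 4 that a real, steady benefit would be missed. That does not follow either. The SAP lists baseline as a time level, and on that reading a step benefit has power .62 to .73 at correlation .5. Even with baseline as covariate only, the same model keeps a treatment-group term, which could detect a constant benefit (.88 in step 5). What the SAP makes conditional on the interaction is the set of follow-up t-tests; it does not say that the group term will be ignored. The sound criticism is that this term's role is not stated.

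It could be argued that .80 was meant for the interaction, since one convention gives .797. That holds only with three time levels. With the four measures that the power sentence names, it gives .905, and the sentence speaks of a comparison between groups.

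Finally, the primary outcomes are defined as changes over the 9 months, so an averaged difference shifts the question, and estimates with intervals would inform a null result more than prospective power does. Both points are fair. The first is the main cost of the fix; the second does not supply the missing power statement.

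**Conclusion.** The point holds as a mismatch between the power statement and the deciding test. The .80 is right for a group main effect if f = .25 and ρ = .5 are assumed, and it cannot be quoted for the interaction. Nor is the interaction defined well enough to be given one power figure, because baseline has two roles.

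Under the stated assumptions (two-sided .05, N = 80, ρ = .5, .5 SD at 9 months), the interaction over the listed levels has power .51 to .73, depending on shape and on whether a covariate-by-time term is fitted. That range illustrates the gap and does not measure a shortfall.

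This is more than missing detail, because a test already contained in the model, on visits that the SAP already lists, had more power at each correlation checked from .3 to .8 and for both shapes. It should be fixed, but it does not invalidate the design or call for a larger trial.

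**What to change.** Keep N = 80 and revise the SAP's Statistical Methods section as follows.

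1. Label .80 as the power of the between-groups comparison over four measures, and state the effect size and correlation assumed for it.
2. Use baseline as the covariate and not as a time level.
3. For each outcome, name the treatment test and its power. Possible wording: *Treatment is judged by the baseline-adjusted difference between groups averaged over 6 and 9 months. With a two-sided .05 level and an assumed correlation of .5, power is .80 for an average difference of .45 SD with 80 caregivers, or .50 SD with 64 (an assumed 20% loss).*
4. Keep the group-by-time interaction as a secondary test of whether the difference changes over follow-up.

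Adding the 3-month visit to the average is optional. At ρ = .5 it raises power for a step benefit from .88 to .93 and lowers it for build-up from .74 to .63.

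If the sponsor prefers the interaction as the treatment test, the SAP should settle baseline's role, list the visits and report that test's own power as a range under stated assumptions.

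The cost is a SAP revision, with no extra caregivers or visits. It is more than relabelling, because it changes the deciding test: the averaged difference asks whether the arms differ after baseline, not whether the gap changes between visits. It should therefore be settled before outcomes are examined by arm.

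### Baseline is both the covariate and a level of time, so with the terms listed it adjusts nothing in the group-by-time test

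*SAP*

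**What the plan says.** The SAP (Statistical Methods, Analysis) plans repeated measures ANCOVAs for all four outcomes and names no other model for the treatment effect. On baseline it says: "The respective baseline measure of each outcome variable will be included as a covariate in the appropriate analysis". The remaining terms follow: "The other predictors will be treatment group, and time (baseline, 6-months, and 9- months for caregiver outcomes". Baseline therefore appears a second time, as a level of the within-caregiver factor. The test of treatment is then defined: "an interaction term between treatment group and time will be included to examine treatment group-related differences controlling for baseline to later assessments".

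No covariate-by-time term is listed, and nothing removes the baseline score from the responses. The Primary Outcomes section frames the endpoints as change: "The four outcome measures include changes over the 9-month study period for the following scales". For 80 caregivers in all, each measured four times, the Design paragraph gives the power: "a comparison between groups using ANOVA will have .80 power to detect a medium effect size".

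**The concern.** In a repeated measures model the group-by-time test is built only from differences between a caregiver's own visits. A covariate that takes the same value on every row for that caregiver drops out of those differences. Once baseline is also a response level, the interaction compares unadjusted change from baseline, although the SAP presents it as an ANCOVA.

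Two things are at stake. First, the precision that a baseline covariate normally brings is lost. Second, the result depends on how the model is coded. Some analysts will fit only the listed terms and others will use a routine that adds covariate-by-time, so the same data can give different p-values. In addition, the stated power is for a comparison between groups, which is not the test the SAP then plans.

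**Working it through.** **Inputs.** From the SAP: N = 80, 1:1 allocation (40 per arm if exactly balanced), alpha .05, power .80, and a medium effect with no number attached. Assumed, because the documents give no values: effect d = 0.5 SD (f = 0.25), equal correlation r between visits of .3, .5 or .7, complete data, and the same effect at every follow-up.

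**1. The stated power.** For the between-group effect over m visits, lambda = f²·N·m / [1 + (m − 1)r]. With f = .25, m = 4 and r = .5, lambda = .0625 × 80 × 4 / 2.5 = 8.0. On 1 and 78 df this gives power .798, which reproduces .80. At r = .3 it is .893 and at r = .7 it is .708. The figure belongs to the between-group test.

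**2. The cancellation.** Write Y(it) = b·B(i) + group + time + group×time + error. For any two visits s and t, Y(it) − Y(is) contains b·B(i) − b·B(i) = 0. The covariate is absent from every contrast that enters the interaction F. Simulated trials of 80 caregivers with visits at baseline, 6 and 9 months confirm this:

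| Data set | No covariate | Additive covariate | Covariate-by-time added |
|---|---|---|---|
| A | 4.174 | 4.174 | 5.525 |
| B | 2.907 | 2.907 | 2.372 |

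The unlisted term can move F in either direction. In random-intercept fits the interaction coefficients were identical with and without the covariate, and the standard error was unchanged or nearly so (.1986 against .1973 in one fit).

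**3. Power of the planned test (2 df, baseline, 6 and 9 months).** The group-difference profile is (0, .5, .5), with mean 1/3. Its sum of squared deviations is 1/9 + 1/36 + 1/36 = 1/6. Lambda = 20 × (1/6) / (1 − r) = 4.76 / 6.67 / 11.11. On 2 and 156 df power is .475 / .624 / .849. It reaches .80 only at r of about .66 or more. Using all four visits does not help (.46 / .61 / .85).

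**4. Comparators (1 df).** Lambda = effect² / (v × 2/40), where v is the per-caregiver variance in SD² units:

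| Contrast | v | Values of v at r = .3/.5/.7 | Power at r = .3/.5/.7 |
|---|---|---|---|
| Change, mean of 6 and 9 minus baseline | (1+r)/2 + 1 − 2r | 1.05/.75/.45 | .577/.722/.909 |
| Baseline-adjusted mean of 6 and 9 | (1+r)/2 − r² | .56/.50/.36 | .839/.878/.957 |
| Change at 9 months | 2(1 − r) | 1.40/1.00/.60 | .463/.598/.814 |
| Baseline-adjusted 9 months | 1 − r² | .91/.75/.51 | .639/.722/.871 |

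**5. Splitting the gap.** Moving from the 2-df interaction to the 1-df change contrast takes power from .48/.62/.85 to .58/.72/.91. The further rise to .84/.88/.96 comes from a covariate that works. The variance ratios are .56/1.05 = .53, .50/.75 = .67 and .36/.45 = .80.

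**6. If software adds covariate-by-time.** Simulated power of the interaction is .61/.72/.90 (univariate) or .74/.79/.91 (multivariate).

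**7. Validity.** Simulated interaction coefficients averaged .50 for a true .50. Simulated Type I error lay between .048 and .055. Without covariate adjustment, a chance baseline imbalance of 0.3 SD and no treatment effect gives an expected contrast of size .3 × (1 − r) = .21/.15/.09 SD.

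**The case against.** Four points can be made for the plan.

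*Change from baseline is itself a form of control, and it matches the change wording of the Primary Outcomes section.* This is true, and it is why the test is valid. It is still not the covariate adjustment that the SAP promises, and under these assumptions it is less precise.

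*The list of time levels may be a slip, with baseline written where 3 months was meant.* The protocol and SAP schedule follow-up at 3, 6 and 9 months, so this is plausible, but the text does not say it. That reading also brings a different fault: group-by-time over follow-up visits tests only whether the effect changes between them, with about 5% power for a constant effect.

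*The power gap depends on the shape of the effect.* This stands for the averaged contrast. With 0.25 SD at 6 months and 0.5 SD at 9 months, the planned test has .37/.50/.73 and the adjusted mean .60/.65/.79. With an effect at 9 months only, the planned test has .48/.62/.85 and the adjusted mean .31/.35/.45, so the planned test wins. The adjusted 9-month contrast (.64/.72/.87) beats the planned test in all three shapes, though it is below .80 at two of the three correlations.

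*A medium effect could mean f = .25 on the interaction itself.* Power would then be about .99 or higher, but that is a different and larger effect than 0.5 SD at each follow-up, and the SAP does not say which it means.

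The lost adjustment and the dependence on software are also alternatives: each follows from a different way of completing the model. That supports the need to specify it.

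**Conclusion.** The concern holds. As written, the baseline covariate contributes nothing to the test that decides the treatment effect. The cancellation is exact for the classical repeated measures F with complete data and depends on no assumed effect or correlation; with missing visits in a mixed model it would be only approximate.

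The size of the loss does rest on assumptions. For a constant 0.5 SD effect, power is .48/.62/.85 against .84/.88/.96 for the adjusted mean of 6 and 9 months, and only part of that difference is due to the double use of baseline. The .80 in the SAP does not cover the planned test. The harm is to efficiency and clarity, not to validity.

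A lesser point: a group main effect reported from this model would average over baseline too. A constant follow-up effect D would then appear as (0 + D + D)/3 = 2D/3, or 3D/4 with all four visits, with t and p unchanged. The SAP does not name this average as its treatment effect.

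This should be fixed before analysis.

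**What to change.** Give baseline one role and name one treatment contrast.

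- **Preferred:** let time contain follow-up visits only, and enter baseline and baseline-by-time as covariate terms. Define the treatment effect as the baseline-adjusted difference between groups, either averaged over follow-ups or at 9 months, and report it with a 95% confidence interval. Choose between the two in advance, according to when the effect is expected. Do not keep group-by-time as the treatment test in this model.
- **Coherent alternative, closer to the change wording:** keep baseline as a response level, drop the covariate and the claim to adjust for baseline, and name a 1-df change contrast. This accepts the lower power (.58/.72/.91 for the mean of 6 and 9 months; .46/.60/.81 at 9 months).

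In either case, restate the power for the chosen contrast with the effect size and correlation written out. Also state whether the 3-month visit, which is collected but missing from the listed time levels, enters the model.

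The cost is SAP wording only. No new data are needed.

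### The paired t-tests planned after a significant interaction do not test the difference between arms at any visit

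*SAP*

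**What the plan says.** The SAP, Statistical Methods (Design), describes a parallel-group trial: "Caregivers will be randomized into two groups: Experimental In-Home Technology System and Limited In-Home Technology System". On allocation it says "Subjects will be randomized 1:1". No matching of caregivers across arms is described in either document.

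Under Analysis, the treatment effect is judged by a repeated measures ANCOVA with the baseline score as covariate: to "evaluate treatment effects, an interaction term between treatment group and time will be included to examine treatment group-related differences". The next step is conditional on that test: "Each significant interaction will be followed up with paired t-tests to examine treatment differences at each set of time points".

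The only other plan for results by visit is descriptive. Of the summary statistics, the SAP says "These will be summarized overall, by treatment group, by assessment time, and by treatment group and time".

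**The concern.** The follow-up sentence gives a paired test the job of finding treatment differences. The design offers only one kind of pair, two visits of the same caregiver. A paired t-test on such pairs asks whether mean change over time is zero, either within one arm or over both arms pooled, and the SAP does not say which. Neither version asks whether the arms differ. The paired test also drops the baseline covariate used in the main model.

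This is the only planned test of when the arms differ. Two kinds of misreading follow if caregivers in both arms change over the nine months for reasons unrelated to the system:

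- A visit with no arm difference can be flagged, because change reaches significance in one arm and not in the other.
- A visit with a real difference can show the same verdict in both arms, because both improved.

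The reader would still have the interaction test and the arm means, but no estimate or confidence interval for the arm difference at any visit.

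**Working it through.** **1. The plan's own figure.** The SAP claims .80 power for a between-group ANOVA with N = 80, four measures and a medium effect at .05. It gives neither a numeric effect nor a correlation. Assume f = .25 and correlation ρ = .5. The noncentrality is f²·N·m / (1 + (m−1)ρ) = .0625 × 80 × 4 / (1 + 3 × .5) = 20 / 2.5 = 8, on 1 and 78 df. Power is .798, so the figure reproduces under those assumptions. It concerns a comparison between groups, which the paired test is not.

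**2. What each test addresses.** Write μ for the mean in arm E (experimental) or L (limited) at visit k, with 0 for baseline.

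- Paired test within an arm: is μ(arm, k) − μ(arm, 0) = 0?
- Paired test pooled over equal arms: is the average of the two arms' changes = 0?
- Treatment difference at visit k: is μ(E, k) − μ(L, k) = 0, given baseline?

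If both arms drift by the same δ, the first two hypotheses are false and the third is true.

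**3. Closed form at 6 months, no true effect.** Inputs: 40 per arm (80 at 1:1), unit SD, ρ = .5 (assumed). The SD of change is √(2(1−ρ)) = 1. The noncentrality is δ√40, and the critical value is 2.02 on 39 df. At δ = .35 it is .35 × 6.32 = 2.21, which gives a power p of .58 in each arm. The arms are independent, so exactly one is significant with probability 2p(1−p) = 2 × .58 × .42 = .49. The second column of the table repeats this for each drift.

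**4. Conditional on a significant interaction.** The paired tests run only after that result, so the procedure was simulated with that condition: 40,000 runs per setting, compound symmetry, the same drift at 6 and 9 months, and a true effect of .6 SD at 9 months only. The interaction was the group × time F test on baseline, 6 and 9 months, significant in about 79% of trials. *Same verdict* means both arms significant in one direction, or neither significant.

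| Common drift (SD) | 6 months: arms disagree, step 3 formula | 6 months: arms disagree, after significant interaction | 9 months: same verdict, drift toward benefit | 9 months: same verdict, drift against benefit |
|---|---|---|---|---|
| 0 | 10% | 11% | 3% | 3% |
| .2 | 36% | 38% | 16% | 13% |
| .35 | 49% | 51% | 50% | 17% |
| .5 | 23% | 24% | 84% | 6% |
| .7 | 2% | 2% | 99% | 5% |

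The direct test, an ANCOVA of the visit score on group and baseline, is significant at 6 months in 6% and misses the 9-month difference in 5%, whatever the drift. If the paired test is pooled over arms instead, it is significant at 6 months in 5%, 42%, 87%, 99% and 100%, from drift alone.

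**5. No true difference at any visit.** The interaction is significant in about 5% of trials. A significant interaction together with disagreeing paired tests at 6 months occurs in 2.2%, 3.4%, 4.0%, 2.7% and 0.5% at the five drifts. A significant interaction together with a significant direct test occurs in 1.7% to 2.0%. The largest excess is about 4.0 − 2.0 = 2 points per outcome, and at drift .7 the paired rate is the lower one.

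**6. Sensitivity over the same drifts.**

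| Setting | 6 months: arms disagree | 9 months: same verdict, toward / against | Direct test misses at 9 months |
|---|---|---|---|
| Effect .5, ρ = .5 | 2–52% | 6–99% / 6–22% | 9% |
| Effect .6, ρ = .3 | 10–54% | 5–93% / 4–22% | 6% |
| Effect .6, ρ = .7 | 0–46% | 2–100% / 1–11% | 2% |

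Replacing the interaction test by a baseline-adjusted 2-df test on 6 and 9 months moves the paired figures for effect .6 by at most about 3 points.

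**The case against.** Five points can fairly be made for the plan.

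- **The step is secondary.** The interaction is a between-arm test, the paired tests run only after it, and the arm means by visit are reported. This stands. No main conclusion on the four outcomes depends on the paired tests, and the concern is confined to locating the effect in time.
- **False signals are few.** Under no true difference the excess is at most about 2 points, and with no drift the two approaches are about equal. This also stands, and it limits the severity.
- **The large percentages assume that someone compares significance verdicts between arms.** The SAP states no such rule, and an analyst could see from the means that one arm improved more. That is partly right. But the arm means are descriptive, and the plan offers no formal between-arm result by visit to read in place of the verdicts.
- **The scenarios are assumed.** Disagreement at 6 months is a false flag only if there is no effect by then, and every large figure needs non-zero drift. The documents give no drift, correlation or numeric effect. They also give no ground for assuming zero drift over nine months.
- **The wording may be a slip.** *Paired* may have been written for *pairwise*, or the aim may have been within-person comparisons loosely described as treatment differences. Either is possible, so the text does not prove that the wrong test was intended. The sentence still names a test that cannot do the stated job.

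**Conclusion.** The concern holds. As written, the follow-up test does not address the question it is given, and nothing else in the SAP supplies a between-arm test, estimate or confidence interval at a visit. That conclusion follows from the design alone and needs no assumed figure.

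The practical size does rest on assumptions (40 per arm, correlation .5, .6 SD at 9 months only, common drift). Misleading patterns are frequent at 6 months for drift of about .2 to .5 SD in either direction, and at 9 months for drift toward benefit. They are uncommon with no drift or with large drift against benefit. The main treatment test is not affected. This should be fixed before analysis, but it does not threaten the trial.

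**What to change.** Replace the follow-up sentence in SAP, Statistical Methods (Analysis). The new sentence should specify, for each outcome, the baseline-adjusted difference between arms (experimental minus limited) with a 95% CI at each post-baseline visit. The estimates can come from the planned repeated measures ANCOVA, or from an ANCOVA of that visit's score on group and baseline. Label any within-arm change as descriptive. If pairwise between-group comparisons were meant all along, say so; that is a one-word correction. The cost is one sentence of SAP text, with no new data and no change to sample size or conduct.

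A further edit is needed only if a separate issue is also corrected. The SAP lists the time levels as follows: "The other predictors will be treatment group, and time (baseline, 6-months, and 9- months for caregiver outcomes". It also uses baseline as covariate, and the caregivers "complete questionnaires on four separate occasions during this study: baseline, 3-months, 6-months, and 9-months". If the time factor becomes 3, 6 and 9 months with baseline as covariate alone, the interaction tests only whether the effect varies over time. A constant .5 SD effect would then be detected by the interaction in 5% of trials and by the baseline-adjusted group term in 92% (correlation .5). In that case:

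- Name the group term, averaged over the three visits, as the test of treatment effect.
- Report the per-visit differences whether or not the interaction is significant. This matters because the group term has only 28% power for a .6 SD effect at 9 months alone, against 86% for the 9-month contrast.

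That version takes three text edits: the follow-up sentence, the time factor, and the sentence naming the interaction as the treatment test.
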